6.4 Clinical support for AAGA patients

Local care teams at the recruitment centres (or wherever is clinically most appropriate) will maintain responsibility for follow up and management of clinical problems, including AAGA, that are identified through structured follow up as part of the DREAMY research study. Relevant support materials and existing NAP5 guidelines for the care of AAGA patients will be provided to all local investigator centres. Further details on investigation of suspected AAGA patients is provided in [Section 9.3](#) and the NAP5 Anaesthesia Awareness Support Pack can be found here: <http://www.nationalauditprojects.org.uk/NAP5-Anaesthesia-Awareness-Pathway> [NAP5 Anaesthesia Awareness Support Pathway].

6.5 Comparator sample for PTSD follow up at 30 days

To provide a baseline incidence of PTSD symptoms in patients undergoing obstetric surgery under GA but who do not experience AAGA, an initial sample of participants will also be asked to complete the PCL-5 checklist and post-natal risk factors for PTSD questionnaire at 30 days. Data collection for this comparator sample will end once at least 300 participants have provided responses.

[figure not shown]

Figure 3. Flowchart of methodology for local investigators

7 Participant Selection criteria

There will be no exceptions (waivers) to eligibility criteria prior to participant inclusion into the study. Any questions raised about eligibility should be addressed prior to entering the participant.

The eligibility criteria have been carefully considered and are standards used to ensure the study results can be appropriately used to make future treatment decisions for other people with similar disease or medical condition. It is therefore vital that exceptions are not made to the following detailed selection criteria.

All participants that are screened for inclusion into the study must be entered onto the Sponsor screening log JREOLOG0001 and will be assigned a sequential number. Participants will be considered eligible for enrolment into this study if they fulfil all the inclusion criteria and none of the exclusion criteria as defined below.

Eligible participants will be entered onto the Sponsor's Subject ID log JREOLOG0002 and assigned a trial specific Identification number in a pre-agreed format in accordance with site identifier and next sequential numerical value e.g. SG001.

7.1 Inclusion criteria

The aim of the study is to provide an inclusive investigation of AAGA in patients with physiological adaptations of pregnancy.

- Female adults (≥ 18 years) of $\geq 24/40$ gestation
- Receiving GA (de novo or regional anaesthesia converted to GA) for surgery with an obstetric indication
- Informed consent obtained

Eligible obstetric indication surgical procedures (examples, but not limited to): caesarean section (LSCS), manual removal of placenta (MROP), exploration under anaesthesia (EUA).

7.2 Exclusion criteria

- Patients too unwell or confused to be able to complete the questionnaire
- Patient refusal
- General anaesthesia for non-obstetric indication (e.g. colorectal or orthopaedic surgery in a pregnant patient)
- Surgery ≥ 48 hours post-partum
- Unable to communicate verbally/in writing in English language

7.3 Discontinuation/withdrawal of participants

Subjects will be able to withdraw at any time up until they have completed the questionnaires and handed them back to the local study investigators. If after this time they change their mind about their participation, they will need to contact the local investigators who would then either return or confidentially destroy their questionnaire responses and demographic information. Participants may also withdraw from the 30 day follow up process by contacting the DREAMY Research Team.

8 Participant Recruitment process

Participant recruitment at a site will only commence once evidence of the following approval/essential documents are in place:

1. REC approval
2. HRA approval
3. Host site confirmation of capacity and capability

All sites participating in the study will also be asked to provide a copy of the following:

1. Confirmation of participating site R&D approval

All participants who wish to enter the study will be screened and consented by the site Principal Investigator, one of the qualified clinicians involved in the study as Local Investigator or an affiliated Research Nurse.

Participants will be recruited from the study start date. Recruitment will last until 12 months after the first patient is recruited in each site.

Participants should be first recruited during the time period 0-24h following the index GA. Omission of recruitment during 0-24h time window does not exclude patients from eligibility and recruitment can still occur at 24-48h or later. However, such patients will be unable to retrospectively complete the earlier Brice questionnaire(s).

Patients will be approached by anaesthetists (PI and/or Local Investigators) during routine follow up of GA procedures in obstetric patients (between 0-24h and 24-48h following the index GA) and provided with information about the study. Consent for inclusion will be taken prior to questionnaire completion. Consent may be taken by Local Investigators or by designated Research Nurses.

9 Study procedures

9.1 Informed consent

Written, informed consent will be taken from all participants in the study. Information accompanying all study questionnaires will fully explain the purpose of the research and what the data will be used for. A separate Patient Information Sheet (PIS) will be given to each potential study participant, prior to recruitment.

Participants will be approached on the ward by Local Investigators during their post-operative hospital stay. Routine practice, as specified in national UK guidance [OAA/AAGBI 2013], is for a member of the anaesthetic team to approach patients after surgery to obtain feedback and exclude the occurrence of anaesthetic-related complications. Most frequently this clinical follow up occurs within 24 hours of surgery and whilst the patient is on a post-natal ward. Opportunity will be made of this routine visit to allow participants to be introduced to the study, time permitting and as appropriate.

Patients are under no obligation to enter the study and will be informed that they can withdraw at any time during the study, without having to give a reason. Because of the simple, non-interventional nature of the study, it is expected that most potential participants will be able to

decide rapidly whether or not they wish to enrol. However, the research team acknowledge that new mothers may be busy with their babies and may require more time to decide. Consent will be taken by an anaesthetic Local Investigator or designated Research Nurse who will have knowledge of the study and be able to answer any questions that may be asked.

If patients are too unwell to be included in the study during the first 24h following the index GA then they may be approached at a later stage for inclusion in subsequent follow up, with a note of the variance to standard recruitment protocol and reason for this.

9.2 Modified Brice Questionnaire

Screening for AAGA is being assessed in this study using the Brice Questionnaire, which has been adapted from the original published form [Brice 1970] in accordance with common usage [Avidan 2011]. Questions used in the modified Brice questionnaire are available in [Appendix 2](#). Initial screening will be done by local investigator teams, who will be invited to contact the CI or DREAMY Research Team members with any queries regarding Brice response classification. All Local Investigators will be provided with training to ensure that responses are assessed in a consistent manner. In assessing whether a response should be assigned as “Brice positive”, investigators will be instructed to focus on memories of events that could occur only in the operating room during the anaesthetic and surgical periods. Participant reports of memories during the period between "going to sleep" and "waking up" will be taken as “Yes” answers to any of Q3, Q4 or Q5 or “Awareness” to Q6. Any such responses, indicating possible AAGA, require the Local Investigator to follow the Suspected AAGA follow up protocol (see [section 9.3](#)). If an investigator is in any doubt about whether the Brice Questionnaire responses constitute a possible AAGA event, then the responses should be discussed with the local PI and/or CI.

Final classification of Brice responses will be performed by the same expert panel responsible for making final AAGA classification decisions.

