6.2 Data collection procedures

There are three stages to participant data collection:

1. In hospital: Screening for AAGA with modified Brice questionnaires and collection of baseline anaesthetic episode data
2. After hospital: telephone follow up with repetition of the Brice questions at 30 days after the index GA
3. Conditional follow up, dependent upon Brice response: structured interview schedules for participants reporting Suspected AAGA, extended follow up of AAGA patients after 3 months, identification of PTSD risk factors and PTSD symptom screening for 12 months.

Initial AAGA screening will occur at three time intervals following a participant's index GA: 0-24 hours, 24-48 hours and 30 days. 0-24h and 24-48h follow up will consist of a modified Brice questionnaire [Brice 1970, Avidan 2009], including categorical and free text responses (see [Appendix 2](#) for the modified Brice questions). Day 30 (+/- 5 days) follow up will be conducted via telephone (or via email, at participant request) using the same Brice question format and response options. Data collection following discharge of the patient from the local hospital site will be coordinated and conducted by the DREAMY Research Team, rather than local site investigators. Modification to the above timeline for Brice questionnaire administration will only be made in exceptions when patients are unable to provide responses at the pre-specified time points and in agreement with the local PI/CI.

Any patient with Brice questionnaire responses indicating possible recall of events during the anaesthetic episode (hereafter termed "Brice positive") will be provided with a specific structured interview schedule or questionnaire to further delineate the characteristics and psychological response to their experience (adapted from the BAG-RECALL trial [Avidan 2011]). Further repetitions of the Brice questionnaire will not be required after a participant has been declared "Brice positive". See [section 9.2](#) for further detail on Brice questionnaire response classification.

Suspected AAGA face-to-face or telephone structured interview schedules will be organised and led by the DREAMY Research Team and provided at the earliest available opportunity. See [Appendix 4](#) for the structured follow up questions for patients with Suspected AAGA.

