6.3 Analysis of AAGA event proportion

Brice questionnaire and Suspected AAGA follow up responses will be analysed to determine the incidence of suspected AAGA in patients undergoing GA for obstetric indication surgery. An expert panel consisting of a minimum of four assessors – including consultant anaesthetists, DREAMY

study representatives and project board members for NAP5 – will independently evaluate all the responses from patients with possible intraoperative awareness. AAGA events will be graded by consensus opinion in accordance with the Michigan Awareness Classification Instrument [Mashour 2010]. Categorisation for impact on the patient will be in accordance with the NAP5 methodology [NAP5], using the same modified NPSA tool to determine severity of psychological impact. Denominator data, based upon the total number of eligible participants enrolled in the study, will be used to calculate a AAGA event proportion for all recruited patients. Site recruitment logs, detailing numbers of excluded patients or patients that declined to participate, will also be used to provide estimates of how representative this is for all obstetric patients undergoing general anaesthesia. Subgroup analysis for emergency LSCS and other surgical procedures will be performed to determine respective event proportions. Agreement between “Brice positive” classification (based upon Brice questionnaire responses alone) and AAGA classification following full review of the Suspected AAGA follow up responses will be declared.

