No formal estimate is made for the sample size of the baseline comparator group of non-AAGA patients who will be undergoing PTSD screening at 30 days. A lack of clear evidence regarding PTSD prevalence in patients receiving general anaesthesia for obstetric surgery would make such estimations speculative. Therefore, sample size has been preferentially determined by operational issues and consideration of sample size of studies identified in a previous systematic review of post-natal PTSD [Anderson 2012].

12.2.2 *Primary endpoint analysis*

The proportion of obstetric GA patients reporting AAGA will be expressed using binomial confidence intervals and compared with established values (see above for rectification of sample size).

There are three competing hypotheses. First, that the event proportion of Brice positivity in obstetrics is similar to that of the general population (i.e. ~1:660). If so, then we expect ~4 patients (binomial 95% CI 1 – 10). Second, that our incidence of Brice positivity will be similar to Paech’s already reported incidence (i.e. ~1:152 [Paech 2008]). Then we expect ~15 (95% CI 8 – 25) patients. Third, that the ratio between “Brice positive” and spontaneous reporting as in the general population (i.e. 1:660 vs 1:19,000) is maintained for obstetric patients (i.e. ~1:19). Then we expect 118 patients (95% CI 98 – 141). These figures for each of the three possible outcomes will be compared using Fisher’s exact test or chi-squared testing to yield a definitive answer as to which is the most likely hypothesis of the three.

Because we are administering the Brice questionnaire during 0-24h following the index GA (i.e. as soon as possible after GA recovery), we expect to obscure those cases who may otherwise report spontaneously. In other words, we do not expect by our methods to detect spontaneous reporting as such, as the questions will already have been asked. It is possible that some few patients may telephone in after their discharge to report that they now recall AAGA, perhaps triggered by the study, but even that would not fulfil the criterion for spontaneous reporting. We plan to class any such cases as “triggered reporting” and analyse them separately.

Subgroup analysis of the AAGA proportion will be conducted for type and urgency of surgical procedure (including emergency LSCS), de novo conversion from regional anaesthesia to GA and for GA inductions using propofol vs. thiopental.

12.2.3 *Secondary endpoint analysis*

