Appendix 2. Modified Brice questions

1. What is the last thing you remember before going to sleep?

- | | | | |
|------------------------------------|--------------------------|---------------------------|--------------------------|
| Being in the pre-op area |  | Seeing the operating room |  |
| Being with family |  | Hearing voices |  |
| Feeling mask on face |  | Smell of gas |  |
| Burning or stinging in the IV line |  | | |
| Other (Free Text): | | | |

2. What is the first thing you remember after waking up?

- | | | | |
|---------------------------|--------------------------|----------------------------|--------------------------|
| Hearing voices |  | Feeling breathing tube |  |
| Feeling mask on face |  | Feeling pain |  |
| Seeing the operating room |  | Being in the recovery room |  |
| Being with family |  | Being in intensive care |  |
| Nothing |  | | |
| Other (Free Text): | | | |

3. Do you remember anything between going to sleep and waking up?

- | | | | |
|------------------------------|--------------------------|-------------------------------|--------------------------|
| No: |  | | |
| Yes: Hearing voices |  | Hearing events of the surgery |  |
| Unable to move or breathe |  | Anxiety/stress |  |
| Feeling pain |  | Sensation of breathing tube |  |
| Feeling surgery without pain |  | | |
| Other (Free Text): | | | |

4. Did you dream during your procedure?

- | | | | |
|-------------------------|--------------------------|------|--------------------------|
| No: |  | Yes: |  |
| What about (Free Text): | | | |

5. Were your dreams disturbing to you?

- | | | | |
|-----|--------------------------|------|--------------------------|
| No: |  | Yes: |  |
|-----|--------------------------|------|--------------------------|

6. What was the worst thing about your operation?

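### A dream alone can make a woman Brice positive, and the three hypotheses are stated on Brice positivity, with no rule that removes dream-only answers before the comparison

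*Protocol*

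**What the plan says.** **Screening rule.** Section 9.2 counts a memory as reported when there are Yes "answers to any of Q3, Q4 or Q5", or when Awareness is chosen at Q6. Such responses are treated as possible AAGA and lead to the suspected-AAGA follow-up. In Appendix 2, Q4 is "Did you dream during your procedure" and Q5 is "Were your dreams disturbing to you". Neither asks for any content linked to the operation, although Q4 has a free-text field.

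**Limiting instruction.** Just before that rule, the same paragraph tells investigators deciding on Brice positive to "focus on memories of events that could occur only in the operating room during the anaesthetic and surgical periods".

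**What the label means.** Section 6.2 calls women with possible recall Brice positive and adds: "Further repetitions of the Brice questionnaire will not be required after a participant has been declared" positive. Section 6.3 describes the label as "based upon Brice questionnaire responses alone" and contrasts it with the AAGA classification made after full review.

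**Panel.** Section 6.3 states: "AAGA events will be graded by consensus opinion in accordance with the Michigan Awareness Classification Instrument". Section 9.2 gives the same panel the final classification of the Brice responses.

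**Endpoint and comparison.** Section 12.1.1 defines the primary endpoint as the proportion reporting AAGA. In Section 12.2.2 the first hypothesis is "that the event proportion of Brice positivity in obstetrics is similar to that of the general population" (1:660). The second and third set Brice positivity at 1:152 and 1:19. Section 4 presents 1:660 as an AAGA proportion found by Brice questioning, and 1:152 as five cases, two definite and three possible awareness. The 1:19 figure is scaled from AAGA rates.

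**The concern.** Two rules in one paragraph give different answers for the same woman. A dream unconnected with surgery fails the operating-room test but satisfies the Q4 rule, so sites can code it either way.

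The ambiguity reaches the main comparison because the protocol moves between two numerators: AAGA in 12.1.1 and in the panel grading of 6.3, and Brice positivity in the hypotheses of 12.2.2. Section 6.3 plans to report agreement between the two, so the protocol itself regards them as different quantities. If Brice positivity keeps dream-only answers, the comparison sets awareness or any dream against figures described as awareness. The counts that separate the first two hypotheses are small, so few such answers are needed to matter.

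There is also an effect on data collection. A woman labelled positive for a dream at 0–24 h need not be given the remaining Brice questionnaires, so later recall at Q3 may not be recorded on the common instrument.

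**Working it through.** **Inputs.** N = 2250 and the null rate 1:660 (0.15%) come from Section 12.2.1, as does the exact binomial test at one-sided 0.05. The three rates and their expected counts come from Section 12.2.2. The dream-only rate d is an assumption, because the protocol gives none.

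**Step 1: the plan's own counts (N × p).**
- 2250/660 = 3.4. The plan says ~4 (1–10), and 1–10 is the interval for 4 events.
- 2250/152 = 14.8. The Clopper-Pearson limits for 15 events are 8.4–24.7; the plan says ~15 (8–25).
- 2250/19 = 118.4. The limits for 118 events are 98.1–140.6; the plan says 118 (98–141).

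The stated figures are reproduced.

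**Step 2: when 1:660 is rejected.** With p = 1/660, P(7 or more) = 0.058 and P(8 or more) = 0.023. The exact test therefore rejects at 8 or more positives.

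**Step 3: add dream-only positives.** Hold true awareness at 1:660, let no dream-only answer be removed, and let d be the share of women positive only through a dream:

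P(positive) = 1 − (1 − 1/660)(1 − d)

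| d (assumed) | Expected positives | As a ratio | Chance of 8 or more | Relation to the plan's ranges |
|---|---|---|---|---|
| 0 | 3.4 | 1:660 | 2.3% | hypothesis 1 |
| 0.1% | 5.7 | 1:395 | 21% | |
| 0.2% | 7.9 | 1:285 | 53% | |
| 0.3% | 10.1 | 1:223 | 79% | |
| 0.5% | 14.6 | 1:154 | 98% | 97% chance of a count in 8–25 (hypothesis 2) |
| 1% | 25.9 | 1:87 | about 100% | 48% chance of a count in 8–25 |
| 2% | 48.3 | 1:47 | about 100% | between hypotheses 2 and 3 |
| 5% | 115.7 | 1:19.4 | about 100% | 95% chance of a count in 98–141 (hypothesis 3) |
| 10% | 228.1 | 1:9.9 | about 100% | above all three ranges |

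Each ratio is 2250 divided by the expected count.

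**Step 4: tipping points.** Solving the same formula for d:
- 50% chance of rejecting 1:660: d = 0.19%, and 0.0019 × 2250 = about 4 women.
- Expected proportion 1:152: d = 0.51%, about 11 women.
- Expected proportion 1:19: d = 5.1%, about 115 women.

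**Limit of the check.** The threshold of 8 belongs to the test named in 12.2.1. Section 12.2.2 names Fisher's exact or chi-squared testing to compare the hypotheses, so rejection chances under those tests may differ. The expected counts and ratios do not depend on the test.

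**The case against.** The strongest reply is that Q4 and Q5 are only a sensitive trigger. The consequence Section 9.2 attaches to them is the follow-up protocol, while the Brice-positive decision has its own narrower instruction. Local coding is not final, because the panel classifies the Brice responses as well as AAGA, and the free text at Q4 lets it see what the dream was about. The declared endpoint is AAGA, and 12.2.2 opens with that proportion. Section 4 even calls the five earlier obstetric cases Brice positive, which suggests that the authors may use the term for awareness. Further Brice repetitions are not required but not forbidden either, and these women are offered a fuller interview and, at 3 months, a question about further memories.

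Much of this stands. A reader might infer that dreams will decide the primary result, or that the primary endpoint as defined counts dreams. The documents support neither: the endpoint is AAGA, the panel may remove dreams, and the dream rate is unknown. The description of the benchmarks as awareness is this protocol's own; how the cited studies handled dreams cannot be seen here.

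What the reply does not supply is a rule. Nothing tells the panel how to classify a dream-only Yes, and nothing moves the three comparisons from Brice positivity to panel-classified AAGA. An analysis plan or investigator training could add detail, but the protocol has already fixed the screening rule and the hypotheses, and they do not fit together.

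**Conclusion.** The point holds in conditional form. Section 9.2 contains two conflicting rules for dreams, and 12.2.2 states its hypotheses on a quantity that may include dreams, although the endpoint and benchmarks are described as AAGA or awareness.

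The size rests on three assumptions: true awareness of 1:660, no removal of dream-only answers by the panel, and an assumed dream-only rate. Under these, a rate of 0.2–0.5% is enough to move the likely conclusion from hypothesis 1 towards hypothesis 2, and about 5% is needed to resemble hypothesis 3. If the panel removes all dream-only answers, this distortion of the count disappears; the conflict in wording and the stopped repetitions remain.

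**What to change.** **Section 9.2 (with 6.2).** Keep Q4 and Q5 as triggers for the structured interview. Code a Yes to Q4 or Q5 with no recall at Q3 and no Awareness at Q6 as dream only, not Brice positive, unless the panel judges the content to be an operating-room event. Continue the remaining Brice repetitions for these women.

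**Sections 12.1.1 and 12.2.2.** Name panel-classified definite or possible AAGA as the numerator for the primary proportion and for all three comparisons. Report unadjudicated Brice positivity alongside as a secondary result, which still answers the research aim of incidence as found by the questionnaire.

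**Cost.** Wording changes, and one or two extra questionnaires for each dream-only woman: about 11 women at a 0.5% rate (0.005 × 2250), more if dreams are commoner. Because Section 6.2 ties the PCL-5 follow-up and the Brice-negative comparator sample to the label, the revised text should also say where dream-only women fall.

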The Brice questionnaire [Brice 1970] has been used as a common standard in awareness research. Although minor variations have been applied [Avidan 2009], all retain the same five questions on recall of any events between induction of anaesthesia and emergence. Importantly, direct and systematic questioning is applied when using Brice questionnaires, which contrast with spontaneously patient reporting of AAGA in NAP5. This difference in methodology may partly account for the apparent divergence between the proportion of AAGA consistently reported in the overall surgical population with Brice questioning (~1:660) versus that by NAP5 (~1:19,000 overall). Although few studies have compared methods of AAGA testing, the Brice questionnaire is known to detect more cases of AAGA than unstructured direct questioning [Mashour 2013, Mashour 2009], and timing/repetition of Brice questioning may also influence the output [Mashour 2013, Sandin 2007, Davidson 2005, Leslie 2007]. These limitations, coupled with the debated gulf between incidence of AAGA established by Brice responses alone versus spontaneously reported incidence, mean that Brice has been regarded by some as not the “gold standard” methodology it is frequently implied to be [Cook 2015]. However, where Brice is uniquely important is as a common tool for comparison and as a screening method to identify a subpopulation that may be at need of further investigation.

Brice questionnaires have been applied only once before in obstetric patients [Paech 2009]. This observation study was primarily designed to investigate difficult airways in obstetric patients receiving a GA, but Brice questionnaires were also offered up to day two following surgery. A total 763 of 1095 obstetric patients were provided Brice questionnaires, of whom five cases were “Brice positive”, yielding an estimate of AAGA incidence of ~1:152. Of these, two were classed as “definite” and three as possible awareness. This preliminary study indicates that Brice positivity may indeed be much higher than it is in the general population. However, the lack of follow up beyond 48 hours, the wide confidence intervals and the fact that AAGA was not the study’s primary outcome make these results somewhat difficult to interpret.

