12.1 Endpoints

12.1.1 Primary endpoints

The primary endpoint is the proportion of obstetric GA patients reporting AAGA in the included sample.

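### Section 9.2 treats any reported dream as a possible awareness report, and the protocol does not say whether dream-only answers count in the proportion compared with awareness rates of 1:660 and 1:152

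*Protocol*

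**What the plan says.** **The screening rule (Protocol 9.2 and Appendix 2).** When assigning the 'Brice positive' label, investigators are told to "focus on memories of events that could occur only in the operating room during the anaesthetic and surgical periods". The next sentence takes a 'Yes' in the "answers to any of Q3, Q4 or Q5", or 'Awareness' at Q6, as a report of memory from the anaesthetic period, and such answers start the Suspected AAGA follow-up. Q4 in Appendix 2 reads "Did you dream during your procedure". Q5 asks whether the dreams were disturbing.

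**The label (6.2 and 6.3).** Section 6.2 gives the 'Brice positive' label to "Any patient with Brice questionnaire responses indicating possible recall of events during the anaesthetic episode". Section 6.3 describes it as resting on the questionnaire responses alone and plans to report its agreement with the AAGA classification reached after full review.

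**The final decision (9.2).** "Final classification of Brice responses will be performed by the same expert panel responsible for making final AAGA classification decisions". No rule is given for a woman who reports only a dream.

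**The endpoint and comparison (12.1.1, 12.2.1, 12.2.2).** "The primary endpoint is the proportion of obstetric GA patients reporting AAGA in the included sample". The power statement in 12.2.1 concerns Brice-positive AAGA. The first hypothesis in 12.2.2 is that "the event proportion of Brice positivity in obstetrics is similar to that of the general population", taken as about 1:660. The second sets Brice positivity at about 1:152. Section 4 presents both rates as incidences of AAGA; the five cases behind 1:152 were two definite and "three as possible awareness".

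**The concern.** An ordinary dream satisfies one sentence of 9.2 and fails the one before it. A site that follows the Q3–Q6 rule literally will label a dreaming woman 'Brice positive'. A site that follows the operating-room instruction will not.

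This matters because the protocol leaves three counts in play: positives on questionnaire answers alone (6.3), Brice positives as finalised by the panel (9.2), and AAGA as graded by the panel (6.3). Section 12.2.2 opens with reported AAGA and then states its hypotheses as Brice positivity, without saying which count is meant. If the first count is used, or if the panel keeps dream-only answers in the second, the numerator includes dreams while the benchmarks are described as awareness. With 3 or 4 events expected under the first hypothesis, a handful of dreams could decide which hypothesis is favoured.

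**Working it through.** **Inputs.** n = 2250 (12.2.1). Hypothesised rates 1:660, 1:152 and 1:19 (5 and 12.2.2). Exact binomial test, one-sided 0.05 (12.2.1). Dream-only rate *d* among women without awareness: not in the protocol, so a range up to 5% is assumed.

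**Step 1: the protocol's expected counts.** Count = 2250 × rate, with exact 95% limits around the stated count.
- 2250/660 = 3.4; limits for 4 events 1.1 to 10.2 (stated about 4, 1–10)
- 2250/152 = 14.8; limits for 15 events 8.4 to 24.7 (stated about 15, 8–25)
- 2250/19 = 118.4; limits for 118 events 98.1 to 140.6 (stated 118, 98–141)

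All three reproduce.

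**Step 2: the decision point.** At 1:660, P(7 or more) = 5.8% and P(8 or more) = 2.3%, so the exact test rejects 1:660 at 8 events. By binomial likelihood, 8 is also the count at which 1:152 becomes more likely than 1:660. The count at which 1:19 overtakes 1:152 is 51.

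**Step 3: add dream-only answers.** If all are counted, p = a + d − a·d, where *a* is true awareness. For a = 1/660 and d = 0.5%: p = 0.001515 + 0.005 − 0.000008 = 0.006507, or 14.6 events (1:154). P(8 or more) rises from 2.3% to 97.8%.

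Probability (%) that each hypothesis is the most likely of the three:

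| True awareness | Dream-only rate (assumed) | Expected positives | 1:660 | 1:152 | 1:19 |
|---|---|---|---|---|---|
| 1:660 | 0 | 3.4 | 97.7 | 2.3 | 0 |
| 1:660 | 0.25% | 9.0 | 32.0 | 68.0 | 0 |
| 1:660 | 0.5% | 14.6 | 2.2 | 97.8 | 0 |
| 1:660 | 2% | 48.3 | 0 | 63.1 | 36.9 |
| 1:660 | 5% | 115.7 | 0 | 0 | 100 |
| 1:152 | 0 | 14.8 | 2.0 | 98.0 | 0 |
| 1:152 | 0.5% | 26.0 | 0 | 100 | 0 |
| 1:152 | 2% | 59.5 | 0 | 11.6 | 88.4 |
| 1:19 | 0 | 118.4 | 0 | 0 | 100 |
| 1:19 | 0.5% | 129.1 | 0 | 0 | 100 |

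A rate of 0.19% (0.0019 × 2250 = 4.3 women) already gives about a 50% chance of 8 or more when awareness is 1:660.

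**Step 4: allow for the panel.** The dream-only rate that makes 1:660 look exactly like 1:152 is (1/152 − 1/660)/(1 − 1/660) = 0.507%, about 11.4 women. If the panel removes a fraction *f* of dream-only answers, the raw rate needed is 0.507%/(1 − f): 1.0% for f = 50%, 2.5% for 80%, 5.1% for 90%.

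**The case against.** A reader might infer that dreams alone would overturn the primary conclusion. The documents do not support that.

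- **The panel.** Section 9.2 gives final Brice classification to the expert panel, and 6.3 has at least four assessors evaluate every possible case. A 'Yes' at Q4 is a screening trigger and not necessarily a counted event. This stands, and it makes the bias conditional. It does not remove it, because the panel has no rule for dream-only answers and 6.3 keeps a Brice count based on the questionnaire alone.
- **The endpoint wording.** Section 12.1.1 refers to reported AAGA, which can be read as the panel's count. That is a fair reading, but 12.2.2 states its hypotheses in the other term.
- **A reading that reconciles 9.2.** The operating-room instruction may govern the label and the Q3–Q6 rule only the trigger for follow-up. This is plausible and close to what is needed, but the text does not say it.
- **The benchmarks.** The protocol does not show how the studies behind 1:660 and 1:152 handled raw dream answers. It shows only that it describes their results as awareness.
- **The size.** The 0.5% is an assumption, and it changes the favoured hypothesis only if true awareness is near 1:660.

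A reader might also infer that dream-only women distort the later PTSD comparison or should leave follow-up. Section 12.1.2 compares women with confirmed AAGA, so dream-only women do not enter that group unless the panel confirms them. Correcting the numerator requires no change in who is followed up.

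**Conclusion.** The point holds as an internal inconsistency in 9.2 joined to an unfixed numerator in 12.1.1 and 12.2.2. Its effect depends on three things the protocol does not settle: how many women report only a dream, how many of those the panel retains, and which count is tested. If all are counted and true awareness is about 1:660, rates of a few per thousand are enough to favour 1:152 wrongly. If true awareness is 1:152, the favoured hypothesis survives 0.5%, although the expected count rises from 14.8 to 26.0 and the estimated proportion is inflated accordingly. If it is 1:19, 0.5% makes little difference. The matter should be settled before data are seen, because deciding afterwards which dreams count could decide which hypothesis is chosen.

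**What to change.** 1. In 9.2, reconcile the two sentences: a 'Yes' at Q4 or Q5 continues to trigger Suspected AAGA follow-up exactly as now, but a dream-only answer is not in itself a counted event.
2. State that dream-only answers are reported as a separate count and enter the numerator for 12.2.1 and 12.2.2 only if the expert panel classifies them as awareness.
3. In 12.1.1 and 12.2.2, name that panel-classified count as the one compared with 1:660, 1:152 and 1:19. The agreement between questionnaire-only positivity and final classification planned in 6.3 can still be reported.

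The cost is a few sentences and a line in site training. Interview, PCL-5 follow-up and referral stay as they are. The downside is a somewhat smaller count, and awareness that a woman describes only as a dream will depend on the panel's judgement.
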